3.0 SELECTION OF SUBJECTS

Patients: A total of 546 men and women will be recruited from the UW Health academic medical center (e.g., primary care clinics, emergency medicine, and other entities of the University of Wisconsin-Madison for which the HS IRB is the IRB of record). Inclusion criteria:

1. Meet the criteria for at-risk drinking on the AUDIT screening (scoring 8+);
OR respond yes to at least two questions on the AUD DSM-5;
OR report moderate- to high-risk drinking patterns as defined by the NIAAA (i.e. more than 7 drinks per week and 3 on a single day for women; more than 14 drinks per week and 4 on a single day for men)
2. Are interested in learning about ways to reduce drinking and want to reduce or modulate their alcohol use
3. Are 21+ years old
4. Own an iPhone or android smartphone and are willing to download the Tula app
5. Are able to understand and sign an electronic consent form in English

Patients will undergo a 72-hour run-in period. Those who return to the app to submit a baseline and weekly survey during the run-in period will qualify to continue with the study and will be randomized to a study group.

Abuse or dependence on other substances will not exclude patients from participation. Patients whose eligibility screen results suggest the possibility of severe alcohol use disorder (at least 6 of 11 symptoms according to DSM-5 criteria) will be excluded. Patients who report having a current psychotic disorder that would prevent participation, have an acute medical problem requiring immediate hospitalization, or have a known terminal illness will likewise be excluded from the study.

When the study team notifies patients about their eligibility status, the team will encourage all ineligible patients to talk with their primary care provider to address any concerns they have about their alcohol use.

If the following scenarios occur during a patient's study period, the patient will remain enrolled in the study and their circumstances will be documented by the UW study coordinator: (1) is unreachable for follow-up surveys; or (2) becomes incarcerated. In the case of incarceration, no study data will be collected from incarcerated individuals during the time they are in prison or jail.

Protocol

HS IRB #2019-0337
Version 5. 10/17/19
Version 6. 04/07/20
Version 7. 10/09/20
Version 8. 01/26/21
Version 9. 08/18/21
Version 10. 07/13/23

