5.0 INTERVENTION PLAN

All patients enrolled in the study will participate in a 3-month intervention period followed by a 9-month follow-up period, for a total of 12 months. Patients are allowed to continue using Tula after the 12-month period, but will not be asked survey questions after 12 months. Please note that Tula is not a treatment—it is a resource used to help patients reduce their drinking.

All patient subjects will undergo a 72-hour run-in period when they will have access to the basic version of Tula. During this period, potential subjects will be asked to complete the Quick Start checklist items within the 72 hours. The checklist tasks are completing the baseline survey; setting goals for the 90-day active intervention period related to drinking and, optionally, to other aspects of health (e.g., sleep, exercise); completing the first weekly survey; and completing a survey called What Matters to Me, which helps patients think about their current health status and what they would like to change. After 72 hours, patient subjects who complete these tasks will be randomized to one of three groups and receive the appropriate access to Tula features.

Patients in all three groups—regardless of randomization group—will have access to the same static content on Tula, which is described in Section 1, Background and Significance. In addition, patients in all three groups will be asked to complete (1) a weekly survey during the active intervention period and, optionally, to revise the goals they set during the run-in period and (2) quarterly surveys at month 3, 6, 9, and 12. Subjects are free not to answer any survey questions.

Self-monitoring (control) group. Patients of this group will continue receiving regular care from their physician with no interference from the two experimental groups. No data will be shared with other participants. Only the research team will have access to subject data for evaluation purposes.

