Clinically integrated group. In addition to receiving the same static content available to all patients, patients in the clinically integrated group will also have access to a discussion group with others in the group (like the peer-supported group described above) and access to a health coach from the UW Health Wellness Center. Health Coaching at UW Health's Center for Wellness at the American Center is provided by a Certified Wellcoach, either in-person at the American Center or over the phone. Health Coaching sessions are not scheduled via Health Link: Health Coaches directly and independently manage their own client calendars. Patients schedule a session directly with the Health Coach via phone or email. When the Health Coach sees a client for more than one session, they schedule the first session via phone or email, then set up subsequent sessions during the first session. Standard clinical Health Coach appointments are not documented in any way in Health Link, nor will they be for this study; as an out-of-pocket, open-to-the-public service, The Center for Wellness uses an independent third-party system, ActiveNet, for any billing needs.

Patients will be encouraged to participate in up to three in-person or phone visits with the health coach at the beginning, middle, and end of the active 90-day implementation period, with the first visit lasting between 60 and 90 minutes and the other two lasting between 20 and 45 minutes. The health coach will also function as the moderator of the discussion group, as the peer mentor does in the peer-supported group.

Patients will have the option to share selected Tula data with the health coach through a dashboard. When a patient in this group completes a survey, they will be presented with a question: "Do you want to share your responses with the health coach? Yes/No." If the subject responds "yes," their survey responses will populate a dashboard that contains data on drinking days / drinks per day and other data reported via the weekly survey. The health coach will have the option to view the data in the dashboard. Data in the dashboard will not be placed in the patient subject's electronic medical record. However, if the health coach sees any data that is concerning that would normally prompt follow-up within the scope of their clinical role, the health coach will contact and follow-up with the patient subject if such a situation were to arise.

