Patient and clinician decision making	Value and decision framing survey	Patient/ clinician survey	9	Patient: Pretest, 12 months Clinician: during interview at month 36
Mediators				
Relatedness	CHESS Bonding Scale ^{48,65}	Patient survey	5	
Competence	Perceived Competence Scale	Patient survey	4	0, 3, 6, 9, 12 mo.
Autonomous motivation	TSRQ ⁶⁶	Patient survey	6	
Tula use (patients)	Number of days used, number of pages viewed	Server log files	NA	Continuous
Moderators				
Patient characteristics	Race, ethnicity, gender, age	Patient survey	NA	Pretest

Protocol

HS IRB #2019-0337
Version 5. 10/17/19
Version 6. 04/07/20
Version 7. 10/09/20
Version 8. 01/26/21
Version 9. 08/18/21
Version 10. 07/13/23

All survey data collected through Tula is housed on CHESS servers then exported to the UW sponsored Google Drive folder for statistical analyses.

Screening survey: People interested in participating in the study will be directed to take a Qualtrics screening survey hosted on the Web to determine if they are eligible to participate in the study.

Baseline survey. After patient subjects are enrolled in the study, they will be asked to take a baseline survey consisting of demographic questions, medical service utilization, quality of life, a modified version of the Brief Alcohol Monitor, the CHESS bonding scale, the alcohol competence scale, the TSRQ, and the value of Tula. Data from the screening survey will be used as baseline data for the AUDIT, AUD DSM-5, and timeline follow-back. Two additional questions related to the impact of COVID-19 on participants' physical and mental health will be added to the quality of life measures. These questions will operate on a 5-point Likert scale and will be included across all CHESS studies. (See supporting document "4.6.20 Global Health Scale v1.3_COVID.docx").

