8.0 STATISTICAL CONSIDERATIONS

Analyses will assess the effectiveness between the three groups longitudinally on the primary and secondary outcomes.

Descriptive analyses. The research team will use descriptive statistics for all demographic and clinical variables across all three arms. To assess the impact of chance baseline imbalances between arms on intervention effect estimates, variables with noticeable differences will be included as covariates in a sensitivity analysis.

Intervention analyses. The analysis assesses direct treatment effects on patient outcomes over time over the 12-month study period. The research team will construct a longitudinal model of our outcome measures at 0, 1, 2, 3, 4, 5, 6, 7, 8, 9, 10, 11, and 12 months after randomization. The stratification variables will be by clinic, biological sex, and alcohol severity. They will be included as factors in the model and the baseline values of patient outcomes will be included as covariates, with a separate model for each primary outcome (risky drinking patterns, quality of life, and cost). This longitudinal analysis is complicated by the dependence among successive observations made on the same individual. Since complete control of measurement is not possible, there may be incomplete data from individual subjects. Therefore we will conduct a mixed-model analysis of repeated measures based on the general linear model with assessment of various covariance structures (compound symmetric, autoregressive order one, and unstructured). Covariance structure selection will be based on Akaike's information criterion and Schwarz's Bayesian criterion.^{46, 47} Pairwise comparisons between treatment groups and specific treatment time contrasts in the mixed model will be conducted to respond to between-group effects and time-based effects. To address issues of incomplete data we plan to estimate treatment effects according to 4 approaches: intention-to-treat, as-treated, per-protocol, and complier-average causal effect. Missing data patterns will be established from the longitudinal data and will be used to adjust the longitudinal intervention analysis according to pattern-mixture modeling.⁶⁹

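### A drinking report collected from randomised patients before randomisation has no role in the analysis, which gives up precision; change from the screening value may also include regression to the mean

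*Combined protocol and SAP*

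**What the plan says.** All places are in the combined protocol and SAP.

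- **Source of the baseline.** Section 5.0, Baseline survey: "Data from the screening survey will be used as baseline data for the AUDIT, AUD DSM-5, and timeline follow-back". The same section says that interested people are "directed to take a Qualtrics screening survey hosted on the Web to determine if they are eligible to participate in the study". One survey therefore both selects patients and supplies their month-0 drinking.
- **Entry routes.** Section 3.0 admits a patient through any one of three routes: an AUDIT score of 8 or more, at least two DSM-5 items, or "OR report moderate- to high-risk drinking patterns as defined by the NIAAA". Only the third is a threshold on drinks.
- **A second report before randomisation.** Section 3.0: "Those who return to the app to submit a baseline and weekly survey during the run-in period will qualify to continue with the study". Section 5.0 lists "completing the first weekly survey" among the tasks of the 72-hour run-in. Its description of the health coach's dashboard refers to "data on drinking days / drinks per day and other data reported via the weekly survey".
- **Analysis.** Section 8.0, Intervention analyses, models outcomes from month 0 to month 12, adjusts for the baseline value of each outcome, and adds that "specific treatment time contrasts in the mixed model will be conducted to respond to between-group effects and time-based effects". Neither this text nor Table 1 gives the run-in weekly survey a role as baseline, covariate or outcome.

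**The concern.** A 7-day drinking report is noisy: one week is an imperfect guide to a patient's usual level. A second report taken before randomisation would explain more of the between-patient variation and so sharpen the arm comparison. The plan requires patients to submit a survey that carries such a report, but gives it no stated use.

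The second issue is narrower. Where patients qualify because their reported drinking is high, the next report tends to be lower even if nothing has changed. All three arms receive Tula with the same static content, so no arm without the app shows how large that fall would be. Section 8.0 puts month 0 in the outcome series and mentions time-based effects. Any within-group or pooled change measured from month 0 could therefore contain a fall that has nothing to do with the app.

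**Working it through.** **Inputs from the documents (Sections 7.0 and 8.0).** Standardised effect d = 0.23, equivalent to 1.37 risky drinking episodes per month; two-sided alpha 0.0167; power 0.80; 182 per group, allocated 1:1:1; attrition 23%, so 182 × 0.77 ≈ 140 evaluable per group. The implied SD is 1.37 / 0.23 = 5.96 episodes per month.

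**Assumed.** The documents give no correlation between drinking reports. Let r be the correlation of a baseline report with a follow-up report, and of follow-ups with one another. Let b be the correlation between the two baseline reports.

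**The plan's own figure.** A plain two-sample comparison needs n = 2 × ((2.393 + 0.842) / 0.23)² ≈ 396 evaluable per group, or 396 / 0.77 ≈ 515 randomised. This is not 182. A repeated-measures analysis of four follow-ups with one baseline covariate reaches 80% power at 140 evaluable if r is about 0.18 or 0.57, but no r is stated. So 182 can be neither confirmed nor shown to be wrong, and the point does not depend on it.

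**Precision, single follow-up.** Residual variance is 1 − r² with one baseline and 1 − 2r²/(1 + b) with two.

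**Precision, mean of four follow-ups.** The variance factor is (1 + 3r)/4 − r² with one baseline and (1 + 3r)/4 − 2r²/(1 + b) with two. For r = b = 0.5 this is 0.625 − 0.250 = 0.375 against 0.625 − 0.333 = 0.292. Power is Φ(0.23 / √(2 × factor / 140) − 2.393).

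| r | b | Single follow-up: residual variance | Cut | Mean of four: factor | Cut | Power, one → two baselines |
|---|---|---|---|---|---|---|
| 0.3 | 0.3 | 0.910 → 0.862 | 5% | 0.385 → 0.337 | 13% | 0.76 → 0.82 |
| 0.5 | 0.5 | 0.750 → 0.667 | 11% | 0.375 → 0.292 | 22% | 0.77 → 0.88 |
| 0.7 | 0.7 | 0.510 → 0.424 | 17% | 0.285 → 0.199 | 30% | 0.89 → 0.97 |
| 0.5 | 0.7 | 0.750 → 0.706 | 6% | 0.375 → 0.331 | 12% | 0.77 → 0.83 |
| 0.5 | 0.8 | 0.750 → 0.722 | 4% | 0.375 → 0.347 | 7% | 0.77 → 0.81 |

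The last two rows matter because the reports may be close in time. Section 4.0 asks for download within 48 hours of the invitation, and the run-in lasts 72 hours: 120 hours, or 5 days, plus the time taken to review eligibility. If review is prompt, two 7-day windows could overlap. On a slow path, with reminders spread over two weeks, they would not.

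**Regression to the mean.** If every patient were selected by truncation on the same report that serves as month 0, the expected spurious fall would be (1 − r) × SD × φ(z)/P, where P is the proportion of screened people selected. At r = 0.5 and P = 0.3 this is 0.5 × 5.96 × 1.159 ≈ 3.45 episodes per month; at r = 0.8 and P = 0.7 it is 0.2 × 5.96 × 0.497 ≈ 0.59. Both assume that the SD of 5.96 describes this measure.

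A simulation used a stable individual level plus independent weekly noise:

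- Entry by high drinking or by a second measure gave a spurious fall of 1.4 (r = 0.5) or 0.86 (r = 0.7) episodes per month.
- Entry only through the second measure, with error independent of the drinking report, gave about 0.
- The bias of the between-arm contrast was about 0 in every case.

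**The case against.** The strongest reply is that the primary aim and the power statement concern differences between randomised arms, and these are unaffected. That stands. A reader might infer that selection on the screening value biases the primary comparison. It does not, because all arms share it.

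A reader might also infer that the sponsor will present the fall from screening as an effect of Tula. No passage says so. Section 5.0 names self-monitoring as the control group, and the phrase on treatment time contrasts may only mean arm differences at given times. The caution is therefore about what should not be claimed.

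Nor do the documents support a fixed size for regression to the mean. It is tempting to set the expected fall of one heavy-drinking patient against d = 0.23, but the first describes an individual and the second a difference between arm means. Drinks quantity is one of three routes, the mix of routes is not given, and no passage says that this route is scored from the timeline follow-back. Excluding patients with six or more DSM-5 symptoms also trims the upper end, which works the other way where severity tracks drinking.

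On the run-in data, four qualifications stand:

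- That the weekly survey holds drinking quantities is taken from the dashboard description; the items themselves are not shown.
- Section 5.0 lets patients skip any question, so a submitted survey may lack the drinking items.
- The absence of a role is silence, not a stated exclusion. The model includes months 1 and 2, which quarterly surveys cannot supply, so some use of weekly data may be intended.
- Table 1 heads its timing as after randomisation, and Section 6.0 speaks of surveys given in the app. Both sit awkwardly with a screening baseline, but the Baseline survey paragraph is the only specific statement of the source.

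Finally, the run-in report follows access to basic Tula and comes alongside goal-setting. That does not disqualify it as a covariate, since it precedes randomisation. It does make it a poor starting point for time contrasts: early change would be missed, and a weekly item might be compared with a differently worded follow-back.

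**Conclusion.** The point holds as one of efficiency, with a secondary caution. The plan gives no stated role to a pre-randomisation drinking report that its own entry procedure collects. Using it would lower arm-contrast variance by about 11% (single follow-up) or 22% (mean of four) at an assumed correlation of 0.5 throughout, and by about 4–6% or 7–12% if the two baseline reports correlate 0.7 to 0.8 with each other. The gain rests on those unstated correlations, on the weekly survey containing usable drinking items, and on few patients skipping them.

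The randomised contrasts are valid as planned. Within-group or pooled change from month 0 may include regression to the mean, by an amount that depends on the unstated mix of entry routes and may be near zero.

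**What to change.** In Section 8.0, Intervention analyses:

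1. For the drinking outcome, name two baseline covariates: the screening timeline follow-back and drinking from the run-in weekly survey. Where the run-in items were skipped, use simple imputation or a missing indicator so that no randomised patient is dropped. The two instruments need not match for this use.
2. State that effect claims rest on between-arm and arm-by-time contrasts, and that change from screening will not be presented as an effect of Tula. If within-group change is shown, label it descriptive and note that month 0 comes from the eligibility survey.

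The cost is SAP wording and a little analysis work. The plan already requires the run-in survey before randomisation, so no new data collection is needed.

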wellness, such as exercise and sleep; keep track of their progress week by week; and take the weekly survey about factors related to drinking and wellness (mood, sleep, social pressure, etc.)

Information—Participants will see a library of information related to wellness, such as building healthy habits, reducing drinking, food and nutrition, physical activity, etc.

Relaxation—Information on relaxation techniques and audio recordings for meditation and binaural beats.

Strategies—Tips for reducing drinking and meeting other health goals, including “Rethinking Drinking” from National Institute for Alcohol and Alcohol Abuse, cognitive behavioral therapy, and quick tips for building skills related to making changes.

The content of Tula will vary by randomization group in two ways: the in-app communication services participants can access, and whether they work with a health coach, as follows:

- In the self-monitoring group, participants will not have access to a discussion group with others using the app. They will be able to send private messages only to the research coordinator (a member of the research team).
- In the peer-supported group, participants will have access to a discussion group available to all members of the group and moderated by a trained peer specialist. Participants will identify themselves in the discussion group by usernames they create, not by their real names. Participants in this group will be able to send private messages to others in the peer-supported group as well as to the peer moderator. If participants have a question that the peer moderator cannot answer, he or she will refer the question to the research team.
- In the clinically integrated group, participants will have access to a discussion group available to all members of the group and moderated by a health coach. Participants will identify themselves in the discussion group by usernames they create, not by their real names. In addition, patients can send private messages to other members of the clinically integrated group and to the health coach. If participants have a question that the health coach cannot answer, he or she will refer the question to the research team. Participants in this group will be encouraged to have up to three sessions in person or by phone with the health coach at the beginning, middle, and end of the active 90-day implementation period.

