The UW Health Coach at the American Center is not professionally obligated to communicate with a patient's PCP; in most coaching circumstances, the Health Coach would not know the identity of a patient's PCP, and having an established relationship with a PCP is not a prerequisite for inclusion in

Protocol

HS IRB #2019-0337
Version 5. 10/17/19
Version 6. 04/07/20
Version 7. 10/09/20
Version 8. 01/26/21
Version 9. 08/18/21
Version 10. 07/13/23

the study or health coaching in general. That said, there may be circumstances where action/communication may be warranted if a subject discloses information that has a direct bearing on his or her health. The Wellness Center has several primary care providers on site at the American Center that the health coaches involved in this study routinely consult in such circumstances.

This sensitive health information being collected and shared through the Tula dashboard allows the coaches to be better informed and provide more responsive treatment. Information shared via the dashboard serves only to support the intervention and will not be used as study data; no response is expected of the health coach relative to her research role. Health coach communication with a patient in the course of the intervention will be dependent on the individual health coaching plan the patient creates with the support of the health coach in accordance with the Whole Health model used by the health coach. If a patient declines to share data to the dashboard, no data will be transmitted to the dashboard.

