- Participants may send messages when moderators cannot respond quickly. Offering features could produce over reliance on Tula to provide support during periods of distress. Study participants will be told that the moderator of their discussion group will make every effort to follow-up on their messages for support. If the moderator is not immediately available, the app will let the participant know that a moderator is unavailable and if they need immediate assistance they should contact their UW health clinic. To maintain a separation between research and clinical activities, members of the study team will not forward patient messages to the central desk of their UW health clinic.

Additional risks may include:

- Learning about sensitive issues, such as excessive alcohol use, while using the Tula app may cause anxiety, distress, embarrassment, or feelings of sadness. However, patient subjects do not have to answer any questions that they don't want to answer.
- The research team will be collecting information on how the smartphone is used and may discover behavior that raises concern about harm to self or others. If we see anything that

Protocol
HS IRB #2019-0337
Version 5. 10/17/19
Version 6. 04/07/20
Version 7. 10/09/20
Version 8. 01/26/21
Version 9. 08/18/21
Version 10. 07/13/23

suggests that patient subjects or others face imminent risk of harm, we will contact appropriate others to intervene (e.g. the police). Individuals will be told this during informed consent.

- All clinicians who are interviewed will be told that they do not have to answer any questions they do not wish to answer. The study team will have any identifying information coded and removed from transcripts. The code key will be kept separate from the transcripts in a locked cabinet. After transcripts are made from recordings of the interviews, the recordings will be destroyed.

To further protect subject confidentiality, all studies funded by the National Institute of Health are issued a Certificate of Confidentiality which prevents investigators and institutions from being required to release identifiable subject information.

Data Storage and Protection

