7.0 STUDY PARAMETERS

Patients will be block randomized by clinic, sex, and alcohol use severity to control for demographics at a 1:1:1 ratio to be in the self-monitoring, peer-supported Tula, or clinically integrated Tula groups. It's anticipated that 3-7 clinics (defined as having at least 10 patients in the study) with 3-7 clinicians each and 546 patient subjects will be recruited from the participating UW Health clinics. Patients will have access to Tula for up to 48 months, depending on time of enrollment, although the active period of participation is defined as 3 months with follow up through 12 months post enrollment (9 month follow-up). Health coaches will have access to patient-shared Tula data from patients of the clinically integrated Tula group for the duration of the study. The peer mentor will have access to discussion boards and private messages on Tula for the duration of the study for patients in the peer-supported

Protocol
HS IRB #2019-0337
Version 5. 10/17/19
Version 6. 04/07/20
Version 7. 10/09/20
Version 8. 01/26/21
Version 9. 08/18/21
Version 10. 07/13/23

group. The research team will have access to all Tula data for all subjects in all groups for the duration of the study.

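### The stated in-app unavailability notice is tied to a discussion-group moderator, so it does not reach the self-monitoring arm's message channel, and wherever it appears it names only the clinic for immediate help

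*Combined protocol and SAP*

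**What the plan says.** The relevant text is in two places in the combined protocol and SAP.

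**The risk and its safeguard (Section 5.0, Potential Risks).** The protocol recognises that "Participants may send messages when moderators cannot respond quickly" and that people may come to rely too heavily on the app when distressed. It gives two safeguards. Participants are told that the moderator of their discussion group will try to follow up. If that moderator cannot be reached at once, "the app will let the participant know that a moderator is unavailable and if they need immediate assistance they should contact their UW health clinic". The same item adds that "members of the study team will not forward patient messages to the central desk of their UW health clinic", so that research and clinical activity stay separate.

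**Who has a moderator (Section 1.0, content of Tula by group).** The peer-supported group has a discussion group moderated by a trained peer specialist. The clinically integrated group has one moderated by a health coach. The third arm has neither: "In the self-monitoring group, participants will not have access to a discussion group with others using the app". Of those participants the protocol says: "They will be able to send private messages only to the research coordinator".

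A separate item under Potential Risks commits the research team to act if it sees anything that "suggests that patient subjects or others face imminent risk of harm, we will contact appropriate others to intervene". That commitment is not limited by arm.

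**The concern.** The safeguard is a specific app rule with a specific trigger, and the trigger does not exist in one of the three arms. A self-monitoring participant can still type a message to a member of the research team, and the protocol text does not say that the app will warn them that nobody may be reading it. Because the study team does not pass messages on to the clinic, someone who needs prompt help that falls short of imminent danger has to seek it personally. An instruction to do so is therefore worth having on every channel.

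The second part concerns the content of the notice. It is meant for someone who needs immediate assistance, yet it names only the clinic. A line written for that situation would ordinarily name emergency services as well.

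What is at stake is participant safety and clarity of instruction. Nothing in the analysis depends on it.

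**Working it through.** No arithmetic applies. The check sets the texts side by side.

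1. **What triggers the notice?** In Potential Risks, the sentence before the notice refers to the moderator of the participant's discussion group, and the notice is shown when that moderator is not immediately available. The trigger is a moderator's unavailability, not an unread message in general.

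2. **Which arms have that moderator?** From Section 1.0:
   - Peer-supported: discussion group, moderated by a peer specialist. The trigger can occur.
   - Clinically integrated: discussion group, moderated by a health coach. The trigger can occur.
   - Self-monitoring: no discussion group; private messages to the research coordinator only. The trigger cannot occur.

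3. **Is an equivalent stated elsewhere for the coordinator channel?** Three places could carry one: the arm description in Section 1.0, the self-monitoring paragraph in Section 5.0, and Potential Risks. None gives an unavailability notice, a response time or a redirection for messages to the coordinator. The monitoring commitments under Potential Risks concern communication between subjects and messages in the support groups. A private message to the coordinator is neither.

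4. **Do the staff-side safeguards do the same job?** Only in part. Escalation of imminent harm covers every arm, and Section 7.0 says: "The research team will have access to all Tula data for all subjects in all groups for the duration of the study". Both work only once someone has looked at the message. Access is not a commitment to read within a given time, and no interval is stated. The notice works differently: it tells the sender what to do before anyone has read anything.

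5. **Which contact does the notice give?** The clinic alone. The police are mentioned in Potential Risks, but as someone the research team may call, not as a contact offered to the participant. The notice names no emergency service in any arm.

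Both parts therefore hold on the protocol text: the notice as written does not reach the coordinator channel, and its only destination is the clinic.

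**The case against.** The strongest reply is that silence in the protocol is not silence to the participant. What people are told about urgent help usually sits in the consent forms and on the app screens, and neither was available here. Section 4.0 says that the second consent is specific to the assigned group and that staff telephone each person after randomization; either could carry the instruction. This stands. It limits the point to what the protocol states. It does not remove it, because Potential Risks sets out an explicit rule, and that rule taken by itself misses a channel.

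It can also be said that the safeguard fits the risk described. The worry is over-reliance on moderators who offer support, whereas the coordinator channel is not presented as a support service and the control arm is promised none. This is fair as an account of the design. But the app still gives self-monitoring participants a place to write, and a line saying that it is not watched continuously would promise them nothing.

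Third, the self-monitoring arm is not without protection. Its patients continue regular care, imminent harm is escalated in every arm, and people whose screening suggests severe alcohol use disorder are excluded. This also stands, and it is why the point is minor.

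A reader might go further and infer that some participants have no UW clinic to call, because the protocol says that "having an established relationship with a PCP is not a prerequisite for inclusion in" the study and keeps enrolled those who stop treatment at a participating clinic. The documents do not support that. The first remark explains why a health coach may not know a patient's primary care provider, and leaving one participating clinic is not the same as having no UW clinic. Recruitment is from UW Health, and a home clinic is asked for at baseline.

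**Conclusion.** The point holds as a minor patient-safety improvement. On the protocol text, the unavailability notice cannot appear on the self-monitoring arm's coordinator channel, and in the arms where it can appear it sends people needing immediate assistance only to their clinic.

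It rests on two things. The first is a reading: Potential Risks speaks of study participants generally and names no arm, so the restriction to two arms follows from combining its reference to a discussion-group moderator with the arm descriptions in Section 1.0. That is the natural reading, but it is an inference. The second is that only the protocol text was available.

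Two stronger conclusions should not be drawn. One is that participants receive no other contact for urgent help; without the consent and app wording, that cannot be known. The other is that the size of the self-monitoring arm measures how many people are exposed. It is only an allocation figure. The documents do not say how many would write to the coordinator in distress while the channel is unattended, so no number at risk can be given.

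No endpoint, estimate, sample size or error rate is affected.

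**What to change.** Amend the notice in Section 5.0, Potential Risks, to a single fixed line shown on every message channel in all three arms, including the coordinator channel. It should say that messages are not continuously monitored and that anyone needing immediate help should call emergency services or contact their clinic. The line should not depend on whether a moderator is available.

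Leave the sentence about moderator follow-up unchanged, so that the control arm is not promised human support that it is not meant to have. Since the line is identical in every arm, the contrast between arms does not change.

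If the group-specific consent or the app already carries such an instruction on all channels, it is enough to say so in Potential Risks.

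The cost is one app-text change and an IRB amendment.
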